	Visit 1 Day -56 to Day -1	Visit 2 Baseline Day 1	Visit 3 Day 14	Visit 4 Day 28	Visit 5 Day 56	Visit 6 Day 84 EOS	Visit 7 Day 7 ⁶	Visit 8 Phone Call Day 30
				(+/-1 day)			(+4 days)	(+/-3 days)
PD Blood Sampling ²		X	X	X	X	X	X	
PK Blood Sampling ²		X	X	X	X	X	X	
Serum Pregnancy	X							
Urine Pregnancy		X	X	X	X	X	X	
Dispense Study Medication		X	X	X	X			
Administration of Morning Dose of ATI-450 in Clinic ⁷		X	X	X	X	X		
Drug Accountability			X	X	X	X		
Adverse Events ⁵	X	X	X	X	X	X	X	X
Prior and Concomitant Medications	X	X	X	X	X	X	X	X

ECG=electrocardiogram, Hep=hepatitis, PD=pharmacodynamic, TB=tuberculosis, EOS=end of study

¹A full physical examination will be performed at screening. The brief physical examination (including signs of CAPS) will be performed at visit 6 and follow-up. Body mass index will be derived in the eCRF.

²On dosing day(s), patient diary, PGA, KSS, vitals, clinical laboratory parameters, PK, and PD will be performed before the administration of study medication.

³Vital signs will be measured prior to dosing and immediately following dosing in a semi supine position after 5 minutes' rest and will include temperature, systolic and diastolic blood pressure, pulse, and respiratory rate.

⁴ A triplicate 12-lead ECG will be recorded after the subject has been resting for at least 5 minutes in a supine position.

⁵Serious adverse event reporting will start at the time of consent. Any AE that occurs between the time of consent and dosing on Day 1 will be recorded as medical history. Treatment-emergent AEs will be collected following the first dose of study medication on Day 1.

⁶Patients should not start their anti-IL-1 therapy until all safety follow-up Day 7 assessments have been completed. However, in the event of a safety concern, patients will be allowed to return early or restart their anti-IL-1 therapy early prior to completing the safety follow-up Day 7 visit at the discretion of the investigator.

⁷ The last dose of ATI-450 will be administered in clinic on Day 84. The second dose of ATI-450 is not to be administered on Day 84.

⁸ Patients will be instructed on how to complete their patient diary at the screening visit. Patients will begin completing the patient diary 7 days prior to beginning ATI-450 administration (Day 1), or immediately beginning at the screening visit if the Day 1 visit is scheduled to occur less than 7 days after screening.

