3 STUDY PLAN

3.1 Overall Study Design and Plan

The study visit schedule and planned assessments at each visit are detailed in Table 1.

This is a Phase 2a, open-label, single-arm study to investigate the safety, tolerability, efficacy, PK, and PD of ATI-450 to maintain remission in patients with CAPS previously managed with anti-IL-1 therapy. Up to 10 patients are planned to be enrolled in the study. The study will consist of an up to 8-week screening period, a 12-week treatment period, and a 4-week safety follow-up period. The total duration of the study for patients remaining in the study until their final safety follow-up assessment will be up to 24 weeks.

The investigator will obtain signed informed consent from the patient before any study procedures are performed. For further details regarding the informed consent process, see Section 9.3. During the screening visit each patient will be required to have all assessments performed as outlined in the Schedule of Assessments (Table 1).

Patients whose eligibility is confirmed at baseline will begin dosing ATI-450 tablets (50 mg BID). Such patients will be in protocol-defined remission due to prior treatment with an anti-IL-1 biologic. Dosing will begin on the day that the next dose of their anti-IL-1 therapy is scheduled at which time anti-IL-1 therapy will be discontinued.

The first dose of ATI-450 (50 mg BID) will be taken at the following times (based on anti-IL-1 therapy):

- Anakinra: 24 hours (+/- 1 hour) after last administration or at approximate time of regular anakinra dose.
- Canakinumab: 8 weeks (+/- 1 week) after last administration.
- Rilonacept: 1 week (+/- 1 day) after last administration.

ATI-450 will be administered orally for 12-weeks. Patients will attend clinic visits on Days 14, 28, 56, and 84 (+/-1 day) for safety, efficacy, PK and PD assessments. Patients will begin recording disease symptoms in their daily diary card 7 days prior to beginning administration of ATI-450, or immediately starting at the screening visit if the Day 1 visit is scheduled to occur less than 7 days after the screening visit. Patients will continue to complete their diary until completion of the safety follow up Day 7 visit.

At the end of 12-weeks, Day 84 (+/- 1 day), patients will stop ATI-450 and conduct end of study assessments. Patients will complete safety follow-up visits on site 7 Days (+4 days) after the last dose of ATI-450 and via a phone call 30 Days (+/-3 days) after the last dose.

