3.2 Discussion of Study Design

The study is designed to assess the safety, tolerability, efficacy, PK, and PD of ATI-450 in patients with CAPS.

Many patients with CAPS achieve complete or near complete disease remission with currently available anti-IL-1 therapies. Therefore, the study is designed to minimize patient's time off anti-IL-1 therapy due to potentially harmful long-term complications that can result from prolonged relapse of disease symptoms.

The study is open-label and there is no washout period for anti-IL-1 therapy; patients enrolled in the trial will begin treatment with study medication (Day 1) on the day of their next scheduled dose of anti-IL-1 therapy. At the end of the 12-week treatment period, ATI-450 administration will be discontinued, and patients will delay administration of anti-IL-1 therapy until 7 days (+4 days) after the last dose of ATI-450.

The 12-week treatment period was selected to allow sufficient time to explore the efficacy of ATI-450 in maintaining disease remission, and to adequately rule out the potential for prolonged disease remission caused by the last dose of anti-IL-1 therapy. Due to its long $t_{1/2}$, this is particularly relevant in instances when canakinumab is used.

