4.4 Premature Discontinuation

4.4.1 Premature Discontinuation of Investigational Product

Patients should discontinue ATI-450 if any of the following occurs:

- Serious infection
- Invasive fungal infection
- Malignancy (except for non-melanoma skin cancer)
- Hepatitis B virus reactivation

- Demyelinating disease
- Heart failure
- Lupus-like syndrome
- Hypersensitivity reaction
- Gastrointestinal perforation
- WBC count: $<1\times10^3/\mu$ L
- ANC: $<0.5 \times 10^3 / \mu L$
- Lymphocyte count: $<0.3\times10^3/\mu$ L
- Platelet count: $<50\times10^3/\mu$ L
- Hemoglobin: <6.5 g/dL
- AST or ALT:
 - o ≥5×ULN persisting for 2-weeks after study medication interruption or second occurrence of ≥5×ULN
 - \circ ≥3×ULN and total bilirubin ≥2×ULN or international normalized ratio [INR] >1.5
 - ≥3×ULN with appearance of fatigue, nausea, vomiting, right upper quadrant pain or tenderness, fever, rash, and/or eosinophilia (>5%)
- Serum creatinine: >2×ULN persisting for 2-weeks after study medication interruption or second occurrence of >2×ULN
- Confirmed, active infection with the severe acute respiratory syndrome coronavirus 2 (SARS-CoV-2 virus)
- The patient withdraws his/her consent to participate in the study
- The patient develops an illness that would interfere with his/her continued participation in the study
- The patient is noncompliant with study procedures or medication, in the opinion of the investigator
- The patient is confirmed to be pregnant
- The sponsor or regulatory agency requests withdrawal of the patient

- Severe AEs or SAEs
- Any other reason relating to the patient's safety

The investigator will make every effort to ensure that patients who prematurely discontinue ATI-450 complete the end of study assessments.

Patients who discontinue ATI-450 prematurely may be replaced at discretion of the sponsor.

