5.2 Efficacy Assessments

5.2.1 Physician Completed Efficacy Questionnaire

The Physician's Global Assessment of Autoinflammatory Disease Activity (PGA) is a measure to be completed by the investigator or designee. The PGA uses a 5-point rating scale: absent, minimal, mild, moderate, and severe. The investigator will select a rating based on the patient's current disease activity at the time of the visit.

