5.2.1.1 Maintenance of Disease Remission and Clinical Remission

Maintenance of disease remission will be assessed during the treatment period. Disease remission is defined as having a PGA score of absent or minimal and a hsCRP and SAA value within the normal range (≤10 mg/L) or within 30 percent of the baseline value.

Maintenance of clinical remission will be assessed during the treatment period. Clinical remission is defined as having a PGA score of absent or minimal.

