5.2.1.2 Time to Relapse

Time to relapse will be assessed during the treatment period. Relapse is defined as a two-point worsening on the PGA scale.

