8.4.5 Handling of Missing Values

Missing data will not be imputed for the safety summaries or the efficacy summaries conducted on the PP population.

For efficacy summaries conducted on the ITT population a model based multiple imputation procedure will be used to impute missing data, where appropriate. Rules for imputation of missing efficacy data will be detailed in the SAP.

Patients who prematurely discontinue the study will be evaluated based on the data collected at each visit attended. Data collected during the withdrawal visit will be used as an end of study assessment for these patients. If the withdrawal visit was performed >1 day after the last dose was administered, then the previous visit will be used as the end of study assessment.

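### The previous-visit rule in Section 8.4.5 has no exception for withdrawal because of CAPS relapse and does not bar the pre-dose Day 1 visit, so a patient who relapsed can be scored in remission at end of study

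*Combined protocol and SAP*

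**What the plan says.** Section 8.4.5 evaluates early leavers on the visits they attended and takes the withdrawal visit as their end-of-study assessment. The exception is a withdrawal visit "performed >1 day after the last dose was administered, then the previous visit will be used as the end of study assessment". No reason for leaving is treated differently, and no visit is ruled out as the substitute. Imputation detail is left to the SAP, whose text is not in the combined document.

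Other provisions that matter here:
- **Day 1 state.** Section 4.1 requires a PGA of minimal or less at entry. Section 3.1 says of patients starting ATI-450: "Such patients will be in protocol-defined remission due to prior treatment with an anti-IL-1 biologic".
- **Day 1 timing.** Table 1, footnote 2, says that on dosing days "patient diary, PGA, KSS, vitals, clinical laboratory parameters, PK, and PD will be performed before the administration of study medication".
- **Disease remission (5.2.1.1).** PGA absent or minimal, with hsCRP and SAA no higher than 10 mg/L or "within 30 percent of the baseline value".
- **Relapse (5.2.1.2).** "Relapse is defined as a two-point worsening on the PGA scale", assessed during the treatment period.
- **PP population (8.2).** Only patients who complete 12 weeks of treatment and 4 weeks of follow-up.

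**The concern.** This is a maintenance-of-remission study, so a flare on ATI-450 is the efficacy failure it is meant to detect. Anti-IL-1 therapy is allowed only in screening and follow-up (6.6), so a relapsing patient has to stop ATI-450 to go back to it. Section 3.2 gives investigators a reason not to wait: "the study is designed to minimize patient's time off anti-IL-1 therapy due to potentially harmful long-term complications".

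The PGA is rated only at visits. If a flare begins between visits and the patient is first seen more than a day after the last dose, the visit that recorded the flare is set aside and an earlier one takes its place. The end-of-study remission proportion, which a reader would take as showing whether remission lasted to the end of treatment, can then count that patient as a success.

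**Working it through.** The plan has no figure to reproduce: N is up to 10 by feasibility, with no power calculation (8.3). The check follows the rule through the schedule and then counts its effect.

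**1. Which visit is substituted.** Assessed visits are on Days 1, 14, 28, 56 and 84, so the gaps are 14−1=13, 28−14=14, 56−28=28 and 84−56=28 days. If no visit is missed and the withdrawal visit falls before the next scheduled day, the substituted visit is up to 13−1=12, 27−14=13, 55−28=27 or 83−56=27 days old. A missed visit or a later withdrawal visit makes it older, so these are not upper bounds.

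**2. Leaving before Day 14.** The previous visit is Visit 2.
- PGA: absent or minimal by eligibility, so clinical remission is met.
- hsCRP and SAA: Section 8.1 defines baseline as the last non-missing value on or before the first-dose date. The Day 1 value is therefore its own baseline, the change is 0%, and the laboratory condition is met.
- Result: clinical and disease remission at end of study, from a visit with no ATI-450 exposure.

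**3. Leaving after Day 14.** The same result follows only if the previous on-treatment visit was itself in remission.

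**4. Whether other analyses correct it.**
- PP excludes the patient.
- Time to relapse is limited to the treatment period, so a relapse first rated more than a day after the last dose may not count.
- Multiple imputation applies to missing values, but here the substituted visit supplies one.

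**5. Size.** One patient moves the ITT end-of-study proportion by 1/N: 1/10=10.0 points, 1/8=12.5 and 1/6=16.7. The table takes N=10 and assumes k patients are affected and all others are in remission (exact 95% intervals).

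| k (assumed) | Rule as written | Scored as failures |
|---|---|---|
| 0 | 10/10 = 100% (69.2–100) | 10/10 = 100% (69.2–100) |
| 1 | 10/10 = 100% (69.2–100) | 9/10 = 90% (55.5–99.7) |
| 2 | 10/10 = 100% (69.2–100) | 8/10 = 80% (44.4–97.5) |

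**6. Whether the cut-off is sensible otherwise.** With the half-life of about 9 to 11 h in Section 1.1.3, the drug remaining at 24 h is 2^(−24/9)=15.7% to 2^(−24/11)=22.0%. At 48 h it is 2^(−48/9)=2.5% to 2^(−48/11)=4.9%. For a stop unrelated to efficacy, a visit more than a day after the last dose is largely off drug, so setting it aside is reasonable.

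**The case against.** The best defence is that the rule does useful work. Suppose a patient is rated mild at Day 28, stops, restarts anti-IL-1 and is in remission at a late withdrawal visit. The previous-visit rule correctly records a failure, where the late visit would credit ATI-450 with the effect of rescue. A reader might infer that substitution can only flatter the result; this case shows otherwise. The rule should therefore be kept for other stops.

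A reader might also infer that the failure would be hidden. The documents do not support that. Attended visits stay in the by-visit summaries, the diary gives a daily KSS that is summarised in ITT (5.2.2, 8.4.1), and adverse events leading to discontinuation are listed by patient (8.4.2). With at most 10 patients, a flare could well be noticed. What stands is that the end-of-study proportion itself can still be wrong, and a patient who leaves early contributes few diary weeks.

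A third inference is that the protocol gives no way to stop for relapse. Section 4.4.1 does not name it, and relapse need not reach "Severe AEs or SAEs". The scale is given as follows: "The PGA uses a 5-point rating scale: absent, minimal, mild, moderate, and severe". Two points up from absent is mild and from minimal is moderate, and PGA is a different scale from adverse event severity. But 4.4.1 also has a general safety entry, and 3.1 allows an early restart of anti-IL-1 on safety grounds. Both can cover relapse, and neither conflicts with 3.2.

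Finally, the chain is narrow. It needs withdrawal from the study, a late withdrawal visit, a previous visit in remission, and no contrary SAP rule. For a patient who only stops ATI-450, 4.4.1 asks for end-of-study assessments without saying which visit is scored.

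**Conclusion.** The point holds as a defect in a stated rule. Followed as written, Section 8.4.5 can score a patient who withdrew in relapse as in remission at end of study in ITT. Before Day 14 it does so automatically, from a pre-dose visit, if the withdrawal visit is late. A relapse rated at a scheduled visit, or at a withdrawal visit within a day of the last dose, is counted as observed.

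The size is 10 points per patient at N=10. The number of such patients is unknown, so the contrast of 100% with 90% or 80% is an illustration under assumed counts. Efficacy is secondary in Table 2 and exploratory in the synopsis, and its analysis is descriptive, so the effect is on interpretation and not on a formal test. The conclusion rests on the protocol text alone; a SAP rule could resolve it. Severity is minor to should-fix.

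**What to change.** Amend Section 8.4.5, with a matching line in 8.4.1:

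- (a) Visit 2, being pre-dose, may not serve as the end-of-study assessment. If there is no on-treatment visit, treat end of study as missing.
- (b) If the recorded reason for stopping is CAPS relapse or lack of efficacy, score end of study and the remaining scheduled visits through Day 84 as not in remission, and count the stop as an event in time to relapse.
- (c) Keep the previous-visit rule, subject to (a), for all other stops. This includes patients who restart anti-IL-1 after an unrelated stop such as COVID-19, low ANC or infection. Restarting alone should not make them failures: most patients leaving early would be expected to restart, so that would replace one bias with the opposite one.

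Naming relapse or lack of efficacy in 4.4.1 as a reason for which the investigator may stop, and saying in 3.1 that the safety clause covers it, is an optional clarification.

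The cost is a few sentences, with no new visits or samples; Section 4.4.2 already asks investigators to seek the withdrawal reason. There are two downsides. The remission proportion may be less favourable, and scoring under (b) depends on an investigator-recorded reason in an open-label study.

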8.5 Interim Analysis

This is an open-label study. The safety will be assessed on an ongoing basis during the conduct of the trial. No formal interim analyses will be conducted.

9 ETHICS AND RESPONSIBILITIES

9.1 Good Clinical Practice

This study will be conducted in accordance with the Note for Guidance on GCP ICH Harmonised Tripartite Guideline E6 (R1)/Integrated Addendum E6 (R2); US FDA Code of Federal Regulations (CFR) (Title 21 Parts 50, 56, 312), requirements for the conduct of clinical studies as provided in the EU Directive 2001/20/EC, the general guidelines indicated in the Declaration of Helsinki; and all applicable regulatory requirements.

9.2 Institutional Review Board/Independent Ethics Committee

Before initiating a study, the investigator/institution must have written and dated approval/favorable opinion from the IRB/IEC for the study protocol/amendment(s), written ICF, any ICF updates, patient recruitment procedures (e.g., advertisements), and any written information to be provided to patients and a statement from the IRB/IEC that these comply with GCP requirements (if applicable). A current copy of the IB should be included as part of the written application to the IRB/IEC.

The IRB/IEC approval(s) must identify the protocol version as well as the documents reviewed. Any amendments to the protocol will require IRB/IEC approval before the implementation of the changes made to the study, except for changes necessary to eliminate an immediate hazard to the study patients.

The investigator will be responsible for the following:

- Providing written summaries of the status of the study to the IRB/IEC annually or more frequently in accordance with the requirements, policies, and procedures established by the IRB/IEC
- Notifying the IRB/IEC of SAEs or other significant safety findings, including adverse drug reactions that are both serious and unexpected, as required by IRB/IEC procedures
- Providing oversight of the conduct of the study at the site and adherence to the requirements of all applicable regulations
- Promptly reporting deviations from, or changes to, the protocol to eliminate immediate hazards to the study patients

9.3 Informed Consent

In obtaining and documenting informed consent, the investigator should comply with the applicable regulatory requirement(s) and should adhere to GCP and to the ethical principles that have their origin in the Declaration of Helsinki. Prior to the beginning of the study, the investigator should have the IRB/IEC written approval/favorable opinion of the written ICF and any other written information to be provided to patients.

- The investigator or his/her representative will explain the purpose and nature of the study as well as possible adverse effects to the patient or his/her legally acceptable representative and answer all questions regarding the study.
- Patients must be informed that their participation is voluntary, and consent can be withdrawn at any point.
- Patients or their legally acceptable representative will be required to sign a statement of informed consent that meets the requirements of US FDA CFR Title 21 Part 50, local regulations, ICH guidelines, Health Insurance Portability and Accountability Act (HIPAA) requirements in the US, and the IRB/IEC or study site.
- Prior to a patient's participation in the study, the written ICF should be signed and personally
 dated by the patient or by the patient's legally acceptable representative, and by the person
 who conducted the informed consent discussion.
- The medical record must include a statement that written informed consent was obtained before the patient was enrolled in the study and the date the written consent was obtained.
- The original copy of the signed ICF will be retained at the study site.
- A copy of the ICF and any other written information must be provided to the patient or the patient's legally acceptable representative.
- If the ICF is revised, the revised ICF must have received the IRB/IEC approval/favorable opinion in advance of its use. Patients must be informed of the changes to the ICF and must re-consent to the most current version during their participation in the study. The patient or the patient's legally acceptable representative should be informed in a timely manner if new information becomes available that may be relevant to the patient's willingness to continue participation in the study. The communication of this information should be documented.

A patient who is rescreened is not required to sign another ICF if the rescreening occurs within 30 days of the previous ICF signature date.

9.4 Data Monitoring Committee

There is no data monitoring committee for this study.

9.5 Financing and Insurance

9.5.1 Contractual and Financial Details

The investigator (and/or, as appropriate, the site's administrative representative) and the sponsor will sign a clinical study agreement prior to the start of the study, outlining overall sponsor and investigator responsibilities in relation to the study. The contract should describe whether costs

Version and Date: 2.0 24 Sep 2020 Page 57 of 71

for pharmacy, laboratory, and other protocol-required services are being paid directly or indirectly.

